End-points. Primary end-point: composite outcome of adherence to all secondary CV prevention recommendations 12 months after discharge, including pharmacological therapies, diet, physical activity and participation in cardiac rehabilitation programs. Secondary end-points: adherence to all secondary CV prevention recommendations at 6 months, percentage of patients achieving optimal control of all individual CV risk factors, composite clinical endpoint at 12 months: all-cause death, all-cause rehospitalization, and all-cause emergency department visits, among others.

Statistical analysis. A logistic regression models will be used to evaluate differences in the primary outcome between women and men, as well as in other outcomes. All subjects will be assumed to have a fixed follow-up (12 ± 1 month). Multivariate adjusted models will be used to address any potential confounding in the associations between sex and each of the outcomes. Covariates will be selected based on their pre-defined clinical value and the unbalances observed across groups in the univariate analyses.

Sponsor: Sociedad Española de Cardiología

Funding: ORGANON (Unrestricted grant)

Principal Investigator: [name], PhD

Executive Committee: [name], PhD; [name] [name], PhD, [name] [name], PhD, [name], PhD; [name], PhD

Scientific Committee: [name], PhD; [name] [name], PhD, [name] [name], PhD; [name] [name], PhD, [name], PhD; [name], PhD; [name] [name], PhD; [name] [name], PhD; [name] [name], PhD;

Clinical sites (25)

	C. Autónoma	Hospital	Población
1	Andalucía	Hospital Universitario Virgen Macarena	Sevilla
2	Andalucía	Hospital Universitario Virgen de la Victoria	Málaga
3	Aragón	Hospital Universitario Lozano Blesa	Zaragoza
4	Asturias	Hospital Universitario Central de Asturias	Oviedo
5	Baleares	Hospital Universitari Son Espases	Palma de Mallorca
6	C. La Mancha	Complejo Hospitalario de Toledo	Toledo
7	C. La Mancha	Complejo Hospitalario Universitario de Albacete	Albacete
8	C. León	Hospital Clínico Universitario de Salamanca	Salamanca
9	C. León	Complejo Asistencial Universitario de León	León
10	C. Madrid	Hospital Universitario Fundación Alcorcón	Alcorcón
11	C. Madrid	Hospital Universitario 12 de Octubre	Madrid
12	C. Valenciana	Hospital General Universitario de Alicante	Alicante
13	C. Valenciana	Hospital Clínico Universitario de Valencia	Valencia
14	Canarias	Hospital Universitario de Gran Canaria [name] (*)	Las Palmas de Gran Canaria

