- **Primary endpoint:** Composite outcome of adherence to all secondary CV prevention recommendations at 12 months after discharge. The composite is built as an all-or-nothing response to an adherence $\geq 80\%$ in all prescribed components of the endpoint: pharmacological therapies (MMAS-8), diet, physical activity and participation in a cardiac rehabilitation program. Adherence will be defined as having at least 80% compliance with all CV prevention recommendations; drugs, cardiac rehabilitation program, diet and physical activity)
- Measurement of adherence to secondary prevention recommendations: At least 80% of adherence for the following prescribed recommendations at 6 and 12 months:
 - Diet recommendations
 - Physical activity recommendations
 - Drug prescriptions:
 - o Aspirin for all without contraindications
 - o P2Y₁₂ inhibitors for all, according to the time indicated at discharge (if none, use 12 months)
 - o Statins / other lipid-lowering therapies for all
 - o Any of the following if indicated:
 - Beta blockers (if LVEF <0.40 or HF)
 - Angiotensin-converting enzyme inhibitors or angiotensin receptor blockers (if LVEF <0.40 or HF)
 - Glucose control medications (SGLT2 inhibitors/GLP-1 agonists)

1. Measurement of adherence to pharmacological recommendations:

a) The Morinsky Medication Adherence Scale (MMAS-8).⁷⁷ A total score of all items will be calculated with a sum score ranging from 0 to 8 for adherence. MMAS-8 Score will be calculated if the respondent answers at least 6 of 8 items. MMAS is trichomized in three levels of adherence:

- High adherence (score 8)
- Medium adherence (score, 6 to 7)
- Low adherence (score, <6)

b) Records of dispensations in the pharmacy: This is an indirect method to measure compliance based on evaluating the collection of the medication in the pharmacy. Patients who withdrew all medications during the year will be considered adherent. The information will be checked from the medical history that records the withdrawal of drugs from the pharmacy. This will be done for each of the secondary prevention medications to calculate adherence to each of them (aspirin, P2Y₁₂ inhibitors, statins, and beta blockers or ACE inhibitors).

2. Measurement of adherence to non-pharmacological recommendations:

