6. STATISTICAL ANALYSIS

A minimum sample size of 820 participants (410 per group) was estimated for an expected relative difference in recommendations compliance of the all-or-none composite primary outcome of 20%. An α error of 0.05 and a β error of 0.20 were considered for the sample size. The recommendations compliance was estimated as 42% for women and 52% for men. With the consideration of 20% of lost to follow-up (discontinuations) the total sample size is 984 patients, which is rounded out to 1000 patients (500 women and 500 men). To increase regional representation and allow exploration of potential regional variability, 25 hospitals from all regions in Spain (17 Autonomous Communities) will be invited to participate.

For the description of continuous variables, mean and SD, or median and interquartile range will be used for Gaussian and non-normal distributions, respectively. For describing categorical variables, frequencies and percentages per category will be used. Categorical variables will be compared using the chi² test, whilst continuous variables will be compared using the student *t* test.

Logistic regression models will be used to evaluate differences in binary outcomes between women and men (in hospital AMI management, post discharge MI management). All subjects will be assumed to have a fixed follow-up (12±1 month). Multivariate adjusted models will be used to address any potential confounding in the associations between sex and each of the outcomes. Covariates will be selected based on their pre-defined clinical value and the unbalances observed across groups in the univariate analyses. Linear, multinomial or ordinal regression models would be used in case of continuous, categorical, or ordinal outcomes, respectively.

In addition to the models evaluating the association between sex and outcomes, a predictive model will be conducted to set predictors for the following outcomes:

- 1) a composite of all preventive therapies (all-or-nothing for diet, physical activity, P2Y₁₂ inhibitors, statins, and beta blockers or ACE inhibitors [if prescribed at discharge]), and

- 2) each group of preventive interventions (drugs, cardiac rehab, diet, physical activity)

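### The predictive model's composite outcome omits cardiac rehabilitation and aspirin, so it matches none of the protocol's adherence endpoints

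*Protocol*

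**What the plan says.** Section 6 (Statistical analysis) adds a predictive model to the models that compare the sexes. It has two outcomes.

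- Outcome 1 is "a composite of all preventive therapies (all-or-nothing for diet, physical activity", continuing with P2Y12 inhibitors and then "statins, and beta blockers or ACE inhibitors [if prescribed at discharge".
- Outcome 2 is "each group of preventive interventions (drugs, cardiac rehab, diet, physical activity", each modelled separately.

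The adherence endpoints are defined elsewhere.

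- The Summary describes the primary endpoint as a composite "including pharmacological therapies, diet, physical activity and participation in cardiac rehabilitation programs".
- The Outcome metrics, which follow section 5.3.3, give the same four parts: drugs measured by MMAS-8, then "diet, physical activity and participation in a cardiac rehabilitation program".
- Section 5.3.1 names two co-primaries instead. One is drug adherence by MMAS-8. The other is diet, physical activity and cardiac rehabilitation together.
- The drug list in the Outcome metrics opens with "Aspirin for all without contraindications" and ends with items that apply if indicated, such as "Beta blockers (if LVEF <0.40 or HF").

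**The concern.** Outcome 1 is presented as covering all preventive therapies, but its own list does not. Objective 3 (section 3) asks which factors go with non-adherence to the recommended therapies, with emphasis on socioeconomic and gender factors. A reader of the results would take the predictors of this composite as predictors of the adherence endpoint reported for women and men.

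Under the section 6 list, a patient who attends too few rehabilitation sessions, or does not take aspirin, can still count as adherent in the model. The study's own definition would class that patient as non-adherent. Rehabilitation is also a component for which the Background (section 1) reports a disadvantage for women, so it is an awkward one to leave out of a composite meant to shed light on gender.

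This is not detail left for an analysis plan. The protocol fixes an explicit list, and that list conflicts with its label and with the endpoint definitions.

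**Working it through.** **The plan's own figure.** The only number tied to the composite is the minimum sample size in section 6. Inputs: 42% in women, 52% in men, alpha 0.05, power 80%, equal groups. Sidedness is not stated; the two-sided value reproduces.

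- Without continuity correction: n = [1.960 × √(2 × 0.47 × 0.53) + 0.842 × √(0.42 × 0.58 + 0.52 × 0.48)]² / 0.10² ≈ 390 per group.
- With continuity correction: n' = (n/4) × [1 + √(1 + 4/(n × 0.10))]² ≈ 410 per group, 820 in total, as stated.

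Nothing in this calculation depends on how outcome 1 of the predictive model is defined.

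**Component comparison.**

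| Component | Outcome metrics | Section 6, outcome 1 |
|---|---|---|
| Diet | included | included |
| Physical activity | included | included |
| Cardiac rehabilitation | included | absent |
| Aspirin | included unless contraindicated | absent |
| P2Y12 inhibitor | included | included |
| Lipid lowering | statin or other agent | statin only |
| Beta blocker | own item, if LVEF <0.40 or HF | joined to ACE inhibitor by *or*, if prescribed at discharge |
| ACE inhibitor/ARB | own item, if LVEF <0.40 or HF | ACE inhibitor only, joined as above |
| Glucose-control drugs | if indicated | absent |
| Drug measure | MMAS-8 for the primary endpoint | not named |

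**Does outcome 1 match any of these endpoints?**

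- Four-part composite (Summary, Outcome metrics): no, because rehabilitation is missing.
- Non-pharmacological co-primary (section 5.3.1): no, because rehabilitation is missing and drugs are added.
- Pharmacological co-primary (section 5.3.1): no, because diet and activity are added and drugs are named one by one, whereas MMAS-8 gives one total score.

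The answer is therefore the same whether the single composite or the pair of co-primaries is taken as primary.

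**Drug measure.** Item 1(b) of the Outcome metrics plans pharmacy dispensation records for each drug, so drug-level data will exist. Section 6 does not say whether outcome 1 uses these or MMAS-8. The two follow different rules: item 1(b) requires every medication to have been collected over the year, while the composite uses an 80% threshold. Item 1(b) lists nearly the same drugs as section 6 but includes aspirin, which suggests that its omission from section 6 is a drafting slip.

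**Direction and size.** Removing components from an all-or-nothing rule can only keep or raise the proportion classed as adherent, if the shared components are judged alike. How far it rises depends on how many otherwise adherent patients fail on rehabilitation or aspirin. The protocol gives no component rates, so no figure follows.

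**The case against.** The strongest reply is that little is lost.

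- Outcome 2 models cardiac rehabilitation in its own right.
- Section 5.3.3 separately plans to study delayed return to work against rehabilitation adherence.
- Section 6 lists family responsibilities and work conciliation among the candidate predictors.
- Section 5.3.3 places the predictor analysis among the exploratory outcomes.

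All of this stands, and it sets the limits of the point. Four stronger readings that a reader might infer do not hold.

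- *That predictors of poor rehabilitation attendance are lost, or that Objective 3 cannot be answered.* Outcome 2 addresses rehabilitation directly. Only the composite model is affected.
- *That the plan has no drug-by-drug measure.* Item 1(b) of the Outcome metrics provides one. What is missing is a statement of which measure outcome 1 uses.
- *That the metrics go by indication and the model by discharge prescription, as a clean contrast.* Section 6 does say "beta blockers or ACE inhibitors [if prescribed at discharge", but the Outcome metrics also restrict the composite to prescribed components. They mix the two bases themselves.
- *That a given share of patients would be misclassified.* Any such figure needs an assumed rehabilitation or aspirin rate for which the documents offer no basis. If only prescribed components count, patients not prescribed rehabilitation would not change class at all.

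The objection does not explain why a composite said to cover all preventive therapies leaves two of them out. The protocol gives no reason for a narrower set.

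**Conclusion.** The point holds as a definitional error in the current text. Outcome 1 of the predictive model omits cardiac rehabilitation and aspirin, and more narrowly ARBs, non-statin lipid-lowering drugs and glucose-control drugs. It corresponds to neither the four-part composite nor either co-primary, so its predictors would describe a different outcome from the one compared between women and men.

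The reach is limited to one exploratory model. The primary comparison, the sample size of 820 before allowance for losses, and the single-group models in outcome 2 are unaffected. The size of the discrepancy in patients cannot be stated from the documents. The conclusion rests on the component lists alone and needs no numerical assumption. It should be corrected, but it does not threaten the main result.

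**What to change.** In section 6, define outcome 1 as the same all-or-none adherence endpoint or endpoints used for the comparison between women and men, with the same components, including cardiac rehabilitation and aspirin. Name the drug measure (MMAS-8 or dispensation records). State one drug denominator, and reconcile the prescribed and indicated wordings between the Outcome metrics and section 6. Keep outcome 2 as it is.

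If a narrower composite is intended, give it a name that lists what it contains, state the reason, and do not report it as covering all preventive therapies.

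The cost is a sentence or two in section 6 and a matching clarification in the Outcome metrics. All components are already collected, so neither data collection nor sample size changes.

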Candidate predictors are classified as biological factors (age, sex, risk factors, comorbidities), disease-related (type of MI: STEMI/NSTEMI, LVEF, number of vessels...), pharmacological factors (daily number of drugs, daily number of doses, specific drugs), socio-economic factors (zip code, education level, employment status, wages...) and specific gender issues (family responsibilities, work conciliation...). Special consideration will be given to age due to the high figures of in-hospital mortality in young women.

For women-specific analysis, female specific factors (menarche age, pregnancies, gestational diabetes, menopause...) will be considered.

We will use the *Clinical Outcomes, HElthcare REsource UtilizatioN, and related costs* (COHERENT) model to study the hospital-related healthcare resources (ED visits, specialist visits, re-hospitalizations and urgent procedures) and costs.

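### In the exploratory predictor model, outcome 1 is stricter for patients discharged on a beta blocker or ACE inhibitor, so if drugs are scored one by one that prescription is tied to non-adherence by definition

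*Protocol*

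**What the plan says.** Section 6 of the Protocol plans a predictive model in addition to the models for sex. Its first outcome is "a composite of all preventive therapies (all-or-nothing for diet, physical activity, P2Y₁₂ inhibitors", continuing with "statins, and beta blockers or ACE inhibitors [if prescribed at discharge". The second outcome is each group of interventions taken separately.

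The candidate predictors in the same section include "pharmacological factors (daily number of drugs, daily number of doses, specific drugs" and "disease-related (type of MI: STEMI/NSTEMI, LVEF, number of vessels".

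The outcome metrics that follow section 5.3.3 expect P2Y12 inhibitors and lipid-lowering therapy in all patients, but make two classes conditional: "Beta blockers (if LVEF <0.40 or HF" and "Angiotensin-converting enzyme inhibitors or angiotensin receptor blockers (if LVEF <0.40 or HF".

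Two drug measures are described there. For MMAS-8, "A total score of all items will be calculated with a sum score ranging from 0 to 8 for adherence". For pharmacy dispensing records, "This will be done for each of the secondary prevention medications to calculate adherence to each of them". Section 6 does not say which measure feeds outcome 1.

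**The concern.** An all-or-nothing outcome gets harder to meet with every component added to it. In outcome 1, one component applies to some patients only, and the variable that decides whether it applies is also offered as a predictor. Drug count moves with that prescription, and so may LVEF, because the outcome metrics link the indication for these drugs to low LVEF or heart failure.

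Objective 3 (section 3) asks which factors go with non-adherence, and section 1 says the reasons should be explored so that interventions can be developed. A report that patients on a beta blocker or ACE inhibitor are less adherent could be taken as a finding about behaviour or regimen burden when it reflects only how the outcome is counted.

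**Working it through.** **Plan's own figure.** The Protocol gives no number for the predictive model. Its nearest figure is the sample size for 42% versus 52%, with alpha 0.05 and power 0.80. Two-sided, without continuity correction:

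n = [1.96·√(2·0.47·0.53) + 0.842·√(0.42·0.58 + 0.52·0.48)]² / 0.10² ≈ 390 per group.

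With continuity correction this becomes 410 per group, 820 in total, as stated. The midpoint of the two rates, 47%, is used below only as an anchor. Those rates belong to a different composite, so applying 47% to outcome 1 is an assumption.

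**Counting components, if drugs are scored class by class.**
- Without the conditional prescription: diet, activity, P2Y12 inhibitor, statin = 4.
- With it: 5 if beta blocker/ACE inhibitor counts as one item, 6 if as two. The wording allows either.

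**Simplest case.** Every component is met with the same probability p in all patients, independently. Success is p^4 versus p^5.
- p = 0.80: 41.0% versus 32.8%. Odds ratio for non-adherence = (0.410/0.590)/(0.328/0.672) = 1.42.
- p = 0.90: 65.6% versus 59.0%. Odds ratio 1.32.

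**Allowing within-patient correlation.** Success with k components is the average over a standard normal z of Φ[(Φ⁻¹(p) + √ρ·z)/√(1−ρ)]^k. For each ρ, p is set so that the 4-component composite is met by 47%. Patients with and without the prescription have identical adherence per component, so any odds ratio comes from the definition alone. The last column is the chance that the prescription reaches two-sided 0.05 with 800 evaluable patients (1000 less 20%), split 400/400 by assumption.

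| ρ | p | Success, 5 / 6 components | OR for non-adherence, 5 / 6 versus 4 | Chance of significance, 5 / 6 |
|---|---|---|---|---|
| 0 | 0.828 | 38.9% / 32.2% | 1.39 / 1.87 | 64% / 99% |
| 0.3 | 0.784 | 41.3% / 36.7% | 1.26 / 1.53 | 37% / 84% |
| 0.5 | 0.744 | 42.6% / 39.1% | 1.20 / 1.38 | 24% / 62% |
| 0.8 | 0.651 | 44.5% / 42.5% | 1.11 / 1.20 | 11% / 25% |

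Check of one cell (ρ = 0.5, 5 components): (0.47/0.53)/(0.426/0.574) = 0.887/0.742 = 1.20.

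A second model (beta-binomial, p = 0.80, one extra component) gives odds ratios for success of 0.769 at correlation 0.1 and 0.847 at 0.3, that is 1.30 and 1.18 for non-adherence. Its correlation is on a different scale from ρ in the table.

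**LVEF.** Suppose all patients with LVEF below 0.40 receive the drugs, and a share f of the others do. Success in the others is (1−f)·0.47 + f·b, where b is success with the extra component. With one extra component and ρ = 0.3, b = 0.413. For f = 0.6 this is 0.188 + 0.248 = 0.436, and the odds ratio is (0.436/0.564)/(0.413/0.587) = 1.10. For f = 0, 0.3, 0.6 and 0.8 the odds ratios are 1.26, 1.18, 1.10 and 1.05. With two extra components they are 1.53, 1.35, 1.19 and 1.09.

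**After the fix.** If every patient compared has the same number of components, or each component is modelled only among those to whom it applies, the odds ratio under the same assumptions is 1.00.

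The Protocol gives no value for p, ρ, f or the split; all are assumed.

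**The case against.** The strongest objection is that the mechanism depends on how drugs are scored. The Protocol uses MMAS-8 for its pharmacological co-primary outcome and for the overall composite. That is one score for the whole regimen, so an extra prescription adds no hurdle and the artefact largely goes away. This stands as a condition on the point. It does not remove it: outcome 1 names drug classes one by one, which a global score cannot rate separately, and the dispensing method is calculated per class on the same list plus aspirin.

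It can also be said that separate models are already planned through outcome 2, and that section 5.3.3 evaluates each component. That is true, and the separate diet and activity models are free of the problem, but they leave outcome 1 as it is. Finally, for pure prediction the association is real, because a patient with more to do is less likely to do all of it. That too is fair. The error lies in reading the association as a determinant of adherence.

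Several stronger readings are tempting, and the document does not support them:
- A reader might infer that every additional drug adds a component. Only the beta blocker/ACE inhibitor item is clearly conditional; aspirin and glucose-lowering drugs are not in outcome 1. Drug count is affected only through its correlation with that prescription.
- A reader might infer that low LVEF becomes a predictor by definition. The trigger in section 6 is the prescription itself, and the LVEF rule sits in the separate outcome metrics.
- A reader might infer that the gender and socioeconomic estimates are distorted. Nothing shows this, and if the prescription is in the model its own coefficient would take up most of the effect.
- A reader might extend the point to the pharmacy-dispensing composite in section 5.3.3. It is not named as a predictive-model outcome.

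**Conclusion.** The point holds in a limited form. If outcome 1 is scored class by class, the conditional prescription is associated with non-adherence by definition, and section 6 also admits it as a predictor. With one extra component the odds ratio for non-adherence is about 1.4 if components are independent and about 1.1 to 1.2 with strong within-patient correlation. It is larger if the two classes count separately, and smaller for LVEF if many patients with preserved LVEF also receive these drugs. These sizes rest on assumed inputs, and truly better adherence among patients prescribed these drugs could offset them.

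A reader might set the figures beside the planned difference between women and men and conclude that the main result is threatened. It is not: section 6 keeps the predictive model apart from the sex comparison, and section 5.3.3 lists the predictor assessment as exploratory. This is a worthwhile, low-cost improvement to an exploratory analysis.

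**What to change.** In section 6, state how drug adherence is scored in outcome 1. If it is scored class by class, do one of the following for the predictor analysis:
- stratify by, or adjust for, the number of components that apply to the patient;
- restrict the composite to the components that apply to every patient; or
- model each component among the patients to whom it applies.

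Add that beta blocker/ACE inhibitor prescription, drug count and LVEF will not be interpreted as determinants of adherence from the unadjusted composite. If the two classes count as one component, the number of applicable components is the same variable as the prescription. Under the adjustment option its coefficient then carries the definitional effect and should be left uninterpreted.

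The cost is analysis wording only; no new data are needed and no clinical rule changes. The small downside is a result slightly harder to communicate than one all-or-none proportion.
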